#### 7.3.1 **Outcomes/endpoint variables**

Primary endpoint:

- Levels of knowledge of the risk for hyperglycemia, and risk factors for hyperglycemia, (survey question 4A, 6),
- Levels of knowledge of signs and symptoms of hyperglycemia (survey questions 5A-C), •
- Levels of knowledge of recommendations for monitoring for hyperglycemia prior to, and during, treatment with Pigray (survey questions 8A-C, 10, 15) and
- Levels of knowledge of recommendations for managing hyperglycemia during treatment ٠ with Piqray (survey questions 12-14).

The primary endpoint is a composite endpoint that combines correct responses given by HCPs to questions included in the composite. Specifically, the primary endpoint is a weighted composite knowledge score aggregated across the following survey questions: 4A, 5A-C, 6, 8A-C. 10, and 12-15. It is calculated as the number of all correctly answered questions divided by the number of all answered questions (i.e. questions that were answered either correct and not correct – unanswered questions are excluded).

Success criteria on the primary endpoint is defined as a weighted composite knowledge level of at least 70% across these key questions.

Secondary endpoint questions:

- Levels of reported receipt and reading of the Pigray Prescriber's/HCP Guide for • hyperglycemia, assessed as the percentages of HCPs who report receipt and reading of the same (survey questions 1, 2)
- HCPs' knowledge levels for each survey question regarding knowledge of, and • management of, hyperglycemia, assessed as the percentages of HCPs with correct responses to each question (individual responses to survey questions 4-15)
- The distribution of responses regarding the primary source from which HCPs learned • about the messages included in the Piqray Prescriber's/HCP Guide for Hyperglycemia, assessed as the percentages of HCPs who report using each of the possible sources as the primary source they used (survey question 3).

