#### Table 7-1Outcomes/endpoints collected in the survey

| Study objective domains assessed   | Corresponding variable (original data collected;
all are categorical variables)  | Operational
definition/derivation
"Calculated as the
percentage of HCPs
who" |
|--|---|--|
| HCPs' knowledge of the risk for hyperglycemia and                                      | Knowledge that hyperglycemia is a risk associated with treatment with Piqray (key question)   | "Checked" question 4A  |
| risk factors for
hyperglycemia  | Knowledge that pneumonitis is a risk associated with treatment with Piqray  | "Checked" question 4B  |
|  | Knowledge that severe cutaneous reactions are a risk associated with treatment with Piqray  | "Checked" question 4C  |
|  | Knowledge that suicidal ideation is not a risk associated with treatment with Piqray  | "Not checked" question
4D   |
|  | Knowledge that onychomycosis is not a risk associated with treatment with Piqray  | "Not checked" question 4E  |
|  | Knowledge that being diabetic/pre-diabetic, having a fasting blood glucose >13.9 mmol/L( 250 mg/dL), and being 75 years of age or older are additional risk factors for developing hyperglycemia while taking Piqray (key question) | "Checked" only "body
mass index <30
kg/m  "for question 6              |
| HCPs' knowledge of the
signs and symptoms of  | Knowledge that excessive thirst is a sign/symptom of hyperglycemia (key question)   | "Checked" question 5A  |
| hyperglycemia  | Knowledge that increased frequency or amount of urination is a sign/symptom of hyperglycemia (key question)   | "Checked" question 5B  |
|  | Knowledge that increased appetite with weight loss is a sign/symptom of hyperglycemia (key question)  | "Checked" question 5C  |
|  | Knowledge that inability to swallow is not a sign/symptom of hyperglycemia  | "Not checked" question 5D  |
|  | Knowledge that yellowing of the skin is not a
sign/symptom of hyperglycemia  | "Not checked" question 5E  |
|  | Knowledge that difficulty breathing is a sign/symptom of hyperglycemia (key question)   | "Checked" question 5F  |
|  | Knowledge that nausea and/or vomiting is a sign/symptom of hyperglycemia (key question)   | "Checked" question 5G  |
|  | Knowledge that headache is a sign/symptom of hyperglycemia (key question)   | "Checked" question 5H  |

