#### Planned analyses

Survey administrative details (e.g., the number of invited HCPs, the number and percentage of responding HCPs, the number and percentage of eligible vs. ineligible HCPs, and the number and percentage of HCPs with partially vs. fully completed surveys) and analysis sets will be described overall and by country.

Confidential

Respondent characteristics/covariates will be summarized overall and by country.

Frequencies, percentages, and corresponding 95% 2-sided CI will be used to summarize the primary and secondary endpoints overall and by country. Depending on the final distribution of data within each subgroup, subgroup analyses of primary endpoints may also be analyzed by specialty and experience with Piqray.

For the primary endpoint, the point estimate of the weighted average composite percentage of HCPs who provide correct responses to the key question set will be estimated and assessed against the 70% threshold. Where subgroup analyses have small sample sizes (e.g., less than about 30), the results should be handled with caution. Although the 70% threshold is considered success, the associated confidence intervals for small subgroups will be wide, reflecting imprecision.

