#### [END SURVEY SCREENING QUESTIONS]

#### MAIN SURVEY

[Preamble 1]: These questions are about important product information for Piqray. Please be sure to review all response choices for each question before answering each question.

1. Did you receive the "Piqray Prescriber's/HCP **Guide for Hyperglycemia**" that reminds healthcare professionals about certain how to identify, and manage, hyperglycemia in patients treated with Piqray?

```
🗆 Yes
```

#### □ No → PROCEED TO QUESTION 3

- □ I don't know/am not sure → PROCEED TO QUESTION 3
- 2. Did you read or review the "Piqray Prescriber's/HCP Guide for Hyperglycemia"?
  - Yes, all of it
    Yes, some of it
    No
    I don't know/am not sure
- What is the primary source you use to learn about the indication, precautions for use, and potential risks for Piqray? (please tick only 1 response)

D Piqray Summary of Product Characteristics

- D Piqray Prescriber's/HCP Guide for Hyperglycemia
- National Competent Authority website
- Professional Society or Congress
- □ The Piqray product website
- The European Medicines Agency website
- Clinical practice guidelines
- A representative from Novartis
- □ Other (not listed above)
- □ I do not know/am not sure

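### Seven of the 13 composite items are credited for a tick and no checklist distractor counts, so ticking every box earns 54% toward a 70% success threshold

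*Protocol*

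**What the plan says.** Protocol section 7.3.1 builds the primary endpoint as a "weighted composite knowledge score aggregated across the following survey questions: 4A, 5A-C, 6, 8A-C. 10, and 12-15". The score is "the number of all correctly answered questions divided by the number of all answered questions", with unanswered questions left out. The criterion follows: "Success criteria on the primary endpoint is defined as a weighted composite knowledge level of at least 70% across these key questions". Under Planned analyses in section 7.7.2, it is the point estimate that "will be estimated and assessed against the 70% threshold"; no confidence limit has to clear 70%.

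Table 7-1 gives the scoring. Items 4A, 5A-C and 8A-C are correct when the box is checked. Six other checklist rows (4D, 4E, 5D, 5E, 8D, 8E) are correct when the box is not checked; one of them is "Knowledge that inability to swallow is not a sign/symptom of hyperglycemia". All six are outside the 7.3.1 list and appear only among the per-question secondary results. Table 7-1 and the questionnaire also label 5F, 5G and 5H as key questions, although 7.3.1 does not list them.

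The ENCePP checklist (Annex 2, section 10) answers no on analytic control of outcome misclassification and on sensitivity analyses.

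**The concern.** A checklist tests knowledge only if ticking a wrong box costs something. Here the right boxes count and the wrong ones do not, so a respondent who ticks everything gets the same credit on those seven items as one who knows which boxes apply. More than half of the score can be earned this way, and the remaining six items have two to four content options each, so guessing adds more.

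At stake is the meaning of the primary verdict. The survey is there to judge whether the educational material works. If the no-knowledge score lies close to the success line, a result at or just above 70% says little about what prescribers know.

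A smaller matter concerns 4A. Question 1 describes a guide "that reminds healthcare professionals about certain how to identify, and manage, hyperglycemia in patients treated with Piqray", and only afterwards does 4A ask whether hyperglycemia is a risk of the product. That item is close to free credit.

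**Working it through.** **Inputs.** Item list, scoring and threshold: section 7.3.1 and Table 7-1. Content options (Appendix 13.1): Q6 four, Q10 three, Q12 two, Q13 three or four (one line is printed twice; the randomisation instruction speaks of three), Q14 two, Q15 three. Each of these six also offers 'I don't know/am not sure', taken here as answered and not correct, in line with section 7.7.1. The stress-test respondent ticks every content box in Q4, Q5 and Q8.

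**The plan's own figure.** The protocol states no score expected by chance. Its only calculation for this endpoint is the precision in Table 7-4, which reproduces: 21/30 gives an exact 95% interval of 50.6-85.3 (half-width 17.35, stated 17.4), and 35/50 gives 55.4-82.1 (13.35, stated 13.4). Neither enters the success rule.

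**Step 1, ticking alone.**
- 13 items: 7/13 = 53.8%. The threshold needs 0.70 × 13 = 9.1 items, so (9.1 − 7)/6 = 35% of the other six.
- 16 items (with 5F-H): 10/16 = 62.5%. The threshold needs 11.2 items, so (11.2 − 10)/6 = 20% of the other six.

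**Step 2, ticking plus guessing.** Let G be the expected number correct among Q6, Q10, Q12, Q13, Q14 and Q15, in that order. The score is (7 + G)/13 or (10 + G)/16. Ranges reflect four or three options for Q13.

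- Among content options: G = 1/4 + 1/3 + 1/2 + (1/4 or 1/3) + 1/2 + 1/3 = 2.17 to 2.25.
- Q6 allows several ticks, so ticking all fails it: G = 1.92 to 2.00.
- 'I don't know' chosen as often as any other option: G = 1/5 + 1/4 + 1/3 + (1/5 or 1/4) + 1/3 + 1/4 = 1.57 to 1.62.

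| Behaviour on the six items | 13 items | 16 items |
|---|---|---|
| Guess among content options | 70.5-71.2% | 76.0-76.6% |
| Q6 allows several ticks | 68.6-69.2% | 74.5-75.0% |
| 'I don't know' as likely as any option | 65.9-66.3% | 72.3-72.6% |

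The last two rows vary one assumption at a time. Together they give G = 1.37 to 1.42, that is 64.4-64.7% on 13 items and 71.0-71.4% on 16.

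**Step 3, item 4A.** If 4A is always correct, the other 12 items need a mean of only (9.1 − 1)/12 = 67.5%.

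**Step 4, effect of adding 5D, 5E, 8D and 8E.** Ticking everything fails all four. With guessing among content options:
- 17 items: (7 + G)/17 = 53.9-54.4%.
- 20 items (with 5F-H): (10 + G)/20 = 60.8-61.3%.
- The opposite habit, ticking nothing and guessing, on 17 items: (4 + G)/17 = 36.3-36.8%.

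**The case against.** The strongest objection is that the 13-item score passes 70% by only 0.5 to 1.2 points, and only under the most favourable reading. Table 7-1 credits Q6 when one option alone is checked, and Q6, unlike Q3, prints no one-response limit, so several ticks may be possible. A don't-know option is offered on all six items; a respondent who always uses it scores 7/13 = 53.8%. This stands, and it is why the result is given as a range.

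A reader might infer that a sample with no knowledge would probably be declared a success. If all 30 to 50 respondents ticked everything and guessed among content options, the pooled 13-item score would reach 70% with probability 0.65-0.78 at n = 30 and 0.68-0.83 at n = 50. The documents do not support this as a forecast. Respondents must have prescribed the product within six months, and nothing suggests that all of them would tick indiscriminately. With several ticks allowed in Q6 the probability falls to about 0.12-0.34, and with don't-know as likely as any option to about 0.01 or less. A single tick-everything guesser reaches 70% (10 of 13) with probability only 0.37-0.40 even in the favourable case.

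It would also be wrong to say that the composite contains no distractors. Q6, Q10 and Q12-15 keep wrong options, and the correct answer to Q14 is false. Only the checklist rows are missing.

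Over-ticking would be visible in the per-question secondary results. That helps a careful reader but does not change the success rule.

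**Conclusion.** The point holds as a weakness in how the composite is built. Under any reading of the questionnaire, 7 of 13 items (54%), or 10 of 16 (62.5%) with 5F-H, can be earned by ticking alone. The expected score of a tick-everything guesser is about 66-71% on 13 items and about 72-77% on 16, varying one assumption at a time, against a threshold of 70%. On 13 items that is within about four points of the line on either side; on 16 it is above the line in every case shown.

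The conclusion is that the threshold separates knowledge poorly from indiscriminate ticking. It is not that the survey will succeed falsely, nor that most such respondents would individually pass. The item list, the scoring rule and the threshold are all fixed in the protocol, so this is not a detail left to the statistical analysis plan. The cueing of 4A is secondary.

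**What to change.** Before launch, amend section 7.3.1 and Table 7-1 in two ways.

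1. Add the collected hyperglycemia distractors 5D, 5E, 8D and 8E to the composite, scored correct when not checked. Items 4D and 4E (suicidal ideation, onychomycosis) are better left out, because they lie outside the hyperglycemia objective in section 6.1.
2. State that, once the screen is submitted, an unticked key box counts as not correct rather than unanswered. If blanks were excluded as unanswered, the tick items could never be scored wrong, and the added rows could not be scored correct. The statistical analysis plan could carry this rule, but the first change depends on it.

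Optionally, report the composite without 4A as a sensitivity analysis. Moving Q4 ahead of Q1-3 may not remove the cue, since the study title also names hyperglycemia.

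The cost is small: no new questions and no extra respondents. The item list must be re-agreed with the regulator, and the observed score could move in either direction, since prescribers who leave implausible boxes blank gain credit and those who over-tick lose it.

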## 6.1 **Primary objective**

Assess HCPs' knowledge of the key information included in the Piqray Prescriber's/HCP Guide for hyperglycemia:

- Risk of, and risk factors for, hyperglycemia
- Signs and symptoms of hyperglycemia
- Recommendations for monitoring for hyperglycemia prior to, and during, treatment with Piqray
- Recommendations for managing hyperglycemia during treatment with Piqray

The primary endpoint is a composite endpoint based on the percentages of HCPs with correct responses to all questions included in the composite regarding the above information

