Table 7-4 provides the precision and corresponding 2-sided 95% exact confidence intervals (CI) around expected levels of knowledge by various numbers of completed surveys for this study. With a targeted weighted composite knowledge level of  $\geq$ 70% for the primary endpoint, a sample size of 30 to 50 HCPs allows estimation of a minimum HCP knowledge level of at least 70% with a precision ranging between 13.4%-17.4%. To endeavor to achieve a larger sample than 30-50 completed surveys and improve precision of the knowledge level estimates, recruitment will remain open until the end of the data collection period, and will not be closed early even if 50 completed surveys have been reached sooner.

| Sample | Probable respondent knowledge levels |               |                   |               |                  |               |                  |               |                  |                           |  |
|--------|--------------------------------------|---------------|-------------------|---------------|------------------|---------------|------------------|---------------|------------------|---------------------------|--|
| size   | 50% 60%                              |               | 60%               | 6 70%         |                  | 80%           |                  |               | 90%              |                           |  |
|        | Precisi
on (%)                    | 95%
Cl     | Precisi
on (%) | 95%
CI     | Precision
(%) | 95%
CI     | Precision
(%) | 95%
CI     | Precision
(%) | 95%
Cl                 |  |
| 30     | 18.7                                 | 31.3-
68.7 | 18.4              | 40.6-
77.3 | 17.4             | 50.6-
85.3 | 15.5             | 61.4-
92.3 | 12.2             | 73.5 .
97.9 |  |
| 50     | 14.5                                 | 35.5-
64.5 | 14.2              | 45.2-
73.6 | 13.4             | 55.4-
82.1 | 11.9             | 66.3-
90.0 | 9.3              | 73.2
96.7              |  |
| 100    | 10.2                                 | 39.8-
60.2 | 10.0              | 49.7-
69.7 | 9.4              | 60.0-
78.8 | 8.3              | 70.8-
87.3 | 6.4              | 82.4
95.1              |  |
| 150    | 8.3                                  | 41.7-
58.3 | 8.1               | 51.7-
67.9 | 7.6              | 62.0-
77.2 | 6.7              | 72.7-
86.1 | 5.2              | 84.0
94.3              |  |

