| 200    | 7.2                                  | 42.9-
57.1 | 7.0               | 52.9-
66.8 | 6.6              | 63.1-
76.3 | 5.8              | 73.8-
85.3 | 4.4              | 85.0-
93.8             |  |
| 300    | 5.8                                  | 44.2-
55.8 | 5.7               | 54.2-
65.6 | 5.4              | 64.5-
75.1 | 4.7              | 75.0-
84.4 | 3.6              | 86.0-
93.2             |  |

Table 7-4Precision and 95% confidence intervals for various combinations of
sample size and knowledge levels

Note: Calculated using PASS 13 software (Hintze 2014), exact confidence intervals for one proportion (Clopper-Pearson).

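### The precision in section 7.5 and Table 7-4 is that of one yes/no result per HCP, not of the pooled-answer primary endpoint it is stated for; for that endpoint it is conservative

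*Protocol*

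**What the plan says.** Section 7.3.1 gives the operational definition of the primary endpoint: "It is calculated as the number of all correctly answered questions divided by the number of all answered questions". Unanswered questions are left out, and the items are "aggregated across the following survey questions: 4A, 5A-C, 6, 8A-C. 10, and 12-15". Success is a composite of at least 70%.

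Section 7.5 states that the study size rests on this endpoint. It presents Table 7-4 as precision "around expected levels of knowledge by various numbers of completed surveys for this study", so n counts HCPs. The note to the table names the method: "exact confidence intervals for one proportion (Clopper-Pearson". The text then applies the table to the primary endpoint, in the sentence that opens "With a targeted weighted composite knowledge level of", and quotes a precision of 13.4% to 17.4% for 50 and 30 HCPs.

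Section 7.7.2 (Planned analyses) says that "corresponding 95% 2-sided CI will be used to summarize the primary and secondary endpoints overall and by country". It names neither the interval method nor the unit of analysis.

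Two other places bear on the point. Section 6.1, like the abstract, describes the endpoint through "percentages of HCPs with correct responses to all questions included in the composite". Table 7-1 also marks three items outside the 7.3.1 list as key, for example "Knowledge that difficulty breathing is a sign/symptom of hyperglycemia (key question" (5F), and likewise 5G and 5H. The questionnaire in Appendix 13.1 tags the same three.

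**The concern.** A one-proportion exact interval needs one binary outcome per sampling unit. The composite in 7.3.1 pools about 13 answers from each HCP, and answers from one person are likely to be correlated. Its sampling error therefore depends on three things: the number of HCPs, the number of items, and the within-HCP correlation. Table 7-4 uses only the first. The precision quoted for the primary endpoint is really that of a single survey question, which is a secondary endpoint.

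What is at stake is whether the protocol tells its regulatory reader correctly how precisely 30 to 50 HCPs will estimate the composite, and whether the interval later reported for it matches its definition.

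**Working it through.** **Inputs from the protocol.** Knowledge level p = 0.70; n = 30 and n = 50 completed surveys; 95% two-sided Clopper-Pearson (7.5, Table 7-4). Items per HCP from 7.3.1: 4A (1) + 5A-C (3) + 6 (1) + 8A-C (3) + 10 (1) + 12-15 (4) = 13.

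**Assumptions.** Within-HCP correlation ρ of answers, which the protocol does not give, varied from 0 to 1; 70% correct on every item; all 13 items answered unless stated.

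**Step 1: reproduce the stated figure.** With x = 0.7n, the limits are the 2.5% quantile of Beta(x, n − x + 1) and the 97.5% quantile of Beta(x + 1, n − x).

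- n = 30, x = 21: 50.6 to 85.3, half-width 17.33 (printed 17.4).
- n = 50, x = 35: 55.4 to 82.1, half-width 13.37 (printed 13.4).

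The table is therefore a calculation for one binary result per HCP.

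**Step 2: variance of the pooled composite.** At full completion, Var = p(1 − p)/n × (1 + 12ρ)/13. The last factor is at most 1, and equals 1 only at ρ = 1. The bound does not depend on equal item difficulty: a per-HCP score between 0 and 1 with mean p cannot have variance above p(1 − p).

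**Step 3: half-widths.** Effective n = 13n/(1 + 12ρ), with Clopper-Pearson at that effective n and 70%.

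| ρ | 1 + 12ρ | effective n (30 HCPs) | half-width | effective n (50 HCPs) | half-width |
|---|---|---|---|---|---|
| 0 | 1.0 | 390 | 4.7 | 650 | 3.6 |
| 0.1 | 2.2 | 177.3 | 7.0 | 295.5 | 5.4 |
| 0.2 | 3.4 | 114.7 | 8.7 | 191.2 | 6.7 |
| 0.3 | 4.6 | 84.8 | 10.2 | 141.3 | 7.8 |
| 0.5 | 7.0 | 55.7 | 12.7 | 92.9 | 9.7 |
| 1 | 13.0 | 30 | 17.3 | 50 | 13.4 |

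A t-based interval on n − 1 degrees of freedom gives nearly the same at ρ = 0.1 to 0.3: 7.0 to 10.2 and 5.4 to 7.7. Over that range the stated precision is too large by a factor of about 1.7 (17.4/10.2; 13.4/7.8) to 2.5 (17.4/7.0; 13.4/5.4).

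**Step 4: check by simulation.** Beta-binomial answers, true level 70%, 20,000 runs per setting, with none, 20% or 50% of surveys partial. The Table 7-4 interval (n = HCPs) covered the truth in 99.9% to 100% of runs at ρ = 0.1 and 0.3, and in 99.2% to 99.7% at ρ = 0.5. At ρ = 1 coverage was 94.6% to 97.4%. The one value below 95% was n = 50 with half the surveys partial.

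**Step 5: item count.** With 16 items (5F-H added) the variance factor is (1 + 15ρ)/16. At ρ = 0.1 that is 2.5/16 = 0.156, against 2.2/13 = 0.169. At ρ = 0.3 it is 5.5/16 = 0.344, against 4.6/13 = 0.354. The picture is the same.

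**The case against.** The best defence is that the table may fit another endpoint. If section 6.1 and the abstract mean that an HCP counts as a success only when every composite question is right, the outcome is one yes/no per HCP and Clopper-Pearson on HCPs is correct. That stands as a real conflict in the wording. It does not rescue the table, because 7.3.1 gives the explicit formula and removes unanswered questions from the denominator, which makes sense only for pooled answers.

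It can also be said that the interval method belongs in the statistical analysis plan, which section 7.7 promises and which is not at hand. That is fair for the analysis interval. It does not cover the study-size statement, which quotes a figure in the protocol itself.

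Finally, the practical consequence is small. Success is judged by the point estimate against 70%. The 30 to 50 target also reflects an expected 4-5% response from about 1000 invitations, and recruitment continues past 50 surveys. All of this stands.

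Two stronger readings are tempting, and the documents support neither.

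- A reader might infer that the interval could be wrong in either direction. A too-narrow interval arises only if the 390 or 650 pooled answers (13 × 30, 13 × 50) are treated as independent. Simulated coverage then falls to about 83-85% at ρ = 0.1 and 65-68% at ρ = 0.3. The protocol nowhere proposes this; Table 7-4 uses HCPs, and its error runs to the conservative side.
- A reader might infer that the reported intervals for the primary endpoint, overall and by country, will be wrong. Section 7.7.2 names no method or unit, and Clopper-Pearson appears only as the planning method, so this cannot be concluded.

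**Conclusion.** The stated precision of 13.4% to 17.4% does not describe the endpoint it is attached to. It is the precision of a single binary result per HCP. For the pooled ratio in 7.3.1 at full completion it is a worst case, reached only when the within-HCP correlation is 1. Under an assumed correlation of 0.1 to 0.3, with 13 items at 70% each, the half-width is about 7 to 10 points for 30 HCPs and 5 to 8 for 50. The correlation range is an assumption, so the full range (4.7 to 17.3 and 3.6 to 13.4) should be kept in view.

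The conclusion rests on 7.3.1 being the governing definition. Since section 6.1 and the abstract can be read otherwise, and the item list is 13 in one place and 16 in others, confidence is moderate. The success rule and the recruitment target do not change. This is a should-fix point.

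**What to change.** 1. Reconcile the endpoint wording (pooled ratio in 7.3.1, against the phrasing about all composite questions in 6.1 and the abstract) and the item list (13 items, or 16 with 5F-H). Everything else depends on this.
2. If the pooled ratio stands, relabel Table 7-4 as precision for single-question, receipt and reading percentages. Add a composite line to 7.5 with its assumptions. With 13 items it could read: at 70% correct and within-HCP correlation 0.1 to 0.3, about ±7 to 10 points for 30 HCPs and ±5 to 8 for 50. Recompute it if the list becomes 16.
3. In 7.7.2, state that the composite's 95% interval treats the HCP as the cluster, using either a ratio estimator with linearised standard error and t on n − 1 degrees of freedom, or a bootstrap that resamples HCPs. This closes off analysing pooled answers as independent. Give it by country only where there are enough HCPs: at 4-5% response, Luxembourg (20 potential prescribers) would yield 0.8 to 1.0 respondents and Slovenia (30) 1.2 to 1.5, too few for a between-HCP variance.

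The cost is a few lines of text and slightly more analysis work with standard survey software. No extra data are needed.
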